5.5 Dose Modifications

NOTE: Dose modifications are based on adverse events, which are possibly, probably or definitely related to drug. More than one dose reduction per cycle may occur.

Patients experiencing grade 3 or 4 AE's that are possibly, probably or definitely related to a particular agent(s) requiring dose modifications as per the tables below will have that particular agent(s) held until resolution of the AE. If AE improves to baseline or \leq grade 1 prior to next scheduled dose, treatment should be restarted with a one dose level reduction for the causative drug for the remainder of the cycle. The next cycle will then continue with this reduced dose level. Patients experiencing grade 3 or 4 AEs that are possibly, probably or definitely related to a particular agent(s) which occur on or after the last treatment day of a cycle, will have that particular agent(s) reduced by one dose level beginning with the next cycle.

NOTE: If the AE is attributed to a specific drug, only that drug needs dose reduction. If the AE is possibly attributed to more than one agent, the more likely agent can be first reduced, and then the other drug if the toxicity recurs. If both drugs are equally likely to have contributed to the toxicity, reduce the ixazomib/placebo first.

Once a patient's dose has been reduced, no dose-re-escalation is permitted unless it is clear that the drug was not responsible for the toxicity that led to the dose reduction.

Rev. Add3

A delay of up to 14 days is allowed between cycles. Any delay beyond 14 days should be discussed with the study chair. If treatment has been delayed for > 8 weeks due to treatment related toxicity, the patient will go off study treatment. A treatment delay of greater than 14 days, but no longer than 60 days, is allowed if the delay is unrelated to study treatment.

If ixazomib/placebo is held for toxicity, the patient may restart drug during the same cycle provided there are additional doses left in the cycle.

If there is a delay in obtaining lenalidomide for start of a new cycle, the cycle can be delayed until it is available in order to allow all drugs to be started at the same time. However, if the cycle has already started, treatment may continue and lenalidomide should be started when it becomes available and continue for the remaining days of lenalidomide as per cycle.

PRO-CTCAE data should not be used for determining dose delays or dose modifications or any other protocol directed action.

5.5.1 Ixazomib/Placebo Treatment Adjustment

See table below for ixazomib/placebo treatment adjustment steps

Ixazomib/Placebo Treatment Adjustment Steps	
Starting Dose	4 mg days 1, 8, 15 every 28 days
Dose Level -1	3 mg days 1, 8, 15 every 28 days
Dose Level -2	2.3 mg days 1, 8, 15 every 28 days
Dose Level -3	Discontinue

5.5.2 Lenalidomide Treatment Adjustment

See table below for lenalidomide treatment adjustment steps

Lenalidomide (CC-5013) Treatment Adjustment Steps		
Starting Dose	(For CrCl 30-60 ml/min) 5 mg daily for 28 days	10 mg daily for 28 days
Dose Level -1	5 mg daily for 21 days every 28 days	10 mg daily for 21 days every 28 days
Dose Level -2	2.5 mg daily for 28 days	5 mg daily for 28 days
Dose Level -3	2.5 mg every other day for 28 days	2.5 mg daily for 28 days
Dose Level -4	Discontinue	2.5 mg every other day for 28 days

5.5.3 Dose Modifications for Ixazomib/Placebo and Lenalidomide Based on Toxicity

	At retreatment and Day 2-21 of Cycle	
NCI CTCAE Grade	If attributed to Lenalidomide	If attributed to Ixazomib/Placebo
Sustained (\geq 7 days) \geq Grade 3 neutropenia or \geq Grade 3 neutropenia associated with fever (temperature \geq 38.5° C) or Grade 4 neutropenia	Hold (interrupt dose) and follow CBC on days of scheduled ixazomib/placebo doses. If the toxicity resolves to baseline or \leq grade 2 prior to Day 14 restart lenalidomide at next lower dose level and continue the cycle until Day 14. Start next cycle at the reduced dose level. If neutropenia is the only toxicity for which a dose reduction is required, G-CSF may be used and the lenalidomide dose maintained.	Hold (interrupt dose) and follow CBC on days of scheduled ixazomib/placebo doses. If the toxicity resolves to baseline or \leq grade 2, restart ixazomib/placebo at next lower dose level and continue for rest of cycle as per protocol. Start next cycle at the reduced dose level.
Sustained (\geq 7 days) \geq Grade 3 thrombocytopenia or \geq Grade 3 thrombocytopenia with bleeding or grade 4 thrombocytopenia	Hold (interrupt dose) and follow CBC on days of scheduled ixazomib/placebo doses. If the toxicity resolves to baseline or \leq grade 2 prior to Day 14 restart lenalidomide at next lower dose level and continue the cycle until Day 14. Start next cycle at the reduced dose level.	Hold (interrupt dose) and follow CBC on days of scheduled ixazomib/placebo doses. If the toxicity resolves to baseline or \leq grade 2, restart ixazomib/placebo at next lower dose level and continue for rest of cycle as per protocol. Start next cycle at the reduced dose level.

	At retreatment and Day 2-21 of Cycle	
NCI CTCAE Grade	If attributed to Lenalidomide	If attributed to Ixazomib/Placebo
Infection \geq grade 2 (with normal neutrophil count)	Hold (interrupt dose) and observe. If the toxicity resolves to baseline or \leq grade 1 prior to Day 14 restart lenalidomide at next lower dose level and continue the cycle until Day 14. Start next cycle at the reduced dose level.	Hold (interrupt dose) and follow CBC on days of scheduled ixazomib/placebo doses. If the toxicity resolves to baseline or \leq grade 1, restart ixazomib/placebo at next lower dose level and continue for rest of cycle as per protocol. Start next cycle at the reduced dose level.
Non-blistering rash Grade 2-3	Hold (interrupt dose) and observe. If the toxicity resolves to baseline or \leq grade 1 prior to Day 14 restart lenalidomide at next lower dose level and continue the cycle until Day 14. Start next cycle at the reduced dose level.	Hold (interrupt dose) and observe. If the toxicity resolves to baseline or \leq grade 1, restart ixazomib/placebo at next lower dose level and continue for rest of cycle as per protocol. Start next cycle at the reduced dose level.
Grade 4	Discontinue lenalidomide and do not resume.	
Desquamating (blistering) rash - any Grade	Discontinue lenalidomide.	Start next cycle at the reduced dose level.
Erythema multiforme \geq Grade 3	Discontinue lenalidomide.	Start next cycle at the reduced dose level.
Sinus bradycardia/ other cardiac Arrhythmia Grade 2	Hold (interrupt dose) and observe. If the toxicity resolves to baseline or \leq grade 1 prior to Day 14 restart lenalidomide at next lower dose level and continue the cycle until Day 14. Start next cycle at the reduced dose level.	No dose modifications required
Grade 3-4	Discontinue lenalidomide.	
Allergic reaction or Hypersensitivity Grade 2-3	Hold (interrupt dose) and observe. If the toxicity resolves to baseline or \leq grade 1 prior to Day 14 restart lenalidomide at next lower dose level and continue the cycle until Day 14. Start next cycle at the reduced dose level.	Hold (interrupt dose) and follow on days of scheduled ixazomib/placebo doses. If the toxicity resolves to baseline or \leq grade 1, restart ixazomib/placebo at next lower dose level and continue for rest of cycle as per protocol. Start next cycle at the reduced dose level.

	At retreatment and Day 2-21 of Cycle	
NCI CTCAE Grade	If attributed to Lenalidomide	If attributed to Ixazomib/Placebo
Grade 4	Discontinue lenalidomide.	Discontinue ixazomib/placebo and do not resume.
Constipation Grade 1-2 ≥ Grade 3	Initiate bowel regimen and maintain dose level. Hold (interrupt dose) and observe. If the toxicity resolves to baseline or ≤ grade 1 prior to Day 14 restart lenalidomide at next lower dose level and continue the cycle until Day 14. Start next cycle at the reduced dose level.	Initiate bowel regimen and maintain dose level.
Renal Function CrCl < 30 mL/min*	Hold (interrupt dose) and observe. If the toxicity resolves to baseline or ≤ grade 1 prior to Day 14 restart lenalidomide at next lower dose level and continue the cycle until Day 14. Start next cycle at the reduced dose level.	No dose modifications required
Venous Thrombosis/embolism ≥ Grade 3	Hold (interrupt) dose and start anticoagulation; restart at investigator's discretion after adequate anticoagulation (maintain dose level).	No dose modifications required.
Nervous system toxicity Peripheral neuropathy Grade 1 or 2 without pain Grade >2 or grade 2 with pain Grade 4	Reduce dose of lenalidomide to the next lower dose level. If a patient is already at the lowest drug level, go off treatment. Reduce dose of lenalidomide to the next lower dose level. If a patient is already at the lowest drug level, go off treatment.	Reduce dose of ixazomib/placebo to the next lower dose level. If a patient is already at the lowest drug level, go off treatment. Discontinue ixazomib/placebo until toxicity resolves or returns to baseline. When toxicity resolves, re-initiate ixazomib/placebo at the next lower dose level. If a patient is already at the lowest drug level, go off treatment. Discontinue ixazomib/placebo
Hyperthyroidism or Hypothyroidism	Omit lenalidomide for remainder of cycle, evaluate etiology, and initiate appropriate therapy. Restart lenalidomide next cycle (decrease dose by one dose level).	No dose modifications required

	At retreatment and Day 2-21 of Cycle	
NCI CTCAE Grade	If attributed to Lenalidomide	If attributed to Ixazomib/Placebo
Any other \geq grade 3 non-hematologic toxicity assessed as at least possibly related to the drugs (nausea, emesis and diarrhea included only if the grade persists despite maximal supportive care)	Hold (interrupt dose) and observe if toxicity is thought to be at least possibly related to lenalidomide. If the toxicity resolves to baseline or \leq grade 2 prior to Day 14 restart lenalidomide at next lower dose level and continue the cycle until Day 14. Start next cycle at the reduced dose level.	Hold (interrupt dose) if toxicity is thought to be at least possibly related to ixazomib/placebo. If the toxicity resolves to baseline or \leq grade 2, restart ixazomib/placebo at next lower dose level and continue for rest of cycle as per protocol. Start next cycle at the reduced dose level.

* Creatinine clearance calculation can be made using standard methods, but the same method should be used for the entire duration of the study.

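### Nine lenalidomide cells of the 5.5.3 toxicity table tie in-cycle restart and end of dosing to Day 14, which fits no lenalidomide schedule in the protocol and, for grade 3-4 events, differs from 5.5

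*Combined protocol and SAP*

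**What the plan says.** Section 5.5 gives a general rule for related grade 3 or 4 events. Events "requiring dose modifications as per the tables below will have that particular agent(s) held until resolution of the AE". If the event improves to baseline or to "grade 1 prior to next scheduled dose, treatment should be restarted with a one dose level reduction for the causative drug"; the fuller wording is "treatment should be restarted with a one dose level reduction for the causative drug for the remainder of the cycle". The next cycle then stays at the reduced level.

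The table in 5.5.3 gives rules by toxicity, under a heading that covers retreatment and Days 2-21. Nine lenalidomide cells share one pattern. In six of them recovery must reach baseline or "grade 1 prior to Day 14 restart lenalidomide at next lower dose level and continue the cycle until Day 14". In the other three it must reach baseline or "grade 2 prior to Day 14 restart lenalidomide at next lower dose level and continue the cycle until Day 14". All nine carry the instruction "restart lenalidomide at next lower dose level and continue the cycle until Day 14. Start next cycle at the reduced dose level". In six of the same nine rows the ixazomib/placebo cell also has a restart, worded "restart ixazomib/placebo at next lower dose level and continue for rest of cycle as per protocol".

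Lenalidomide is scheduled daily on days 1-28 (5.1.1 and 8.2.5). The first reduction from the usual starting dose in 5.5.2 is "10 mg daily for 21 days every 28 days". The other active levels run over 28 days, daily or every other day, apart from the matching 21-day level in the reduced-renal-function column.

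**The concern.** A site that holds lenalidomide for one of these nine reasons is told to stop again at Day 14, a day that ends no dosing period defined elsewhere for this drug. If the toxicity resolves on Day 14 or later, the cell does not say what to do in that cycle. For a grade 3 or 4 event, the site can also find a different instruction in 5.5.

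Sites could therefore handle the same event differently while each relies on protocol text. What is at stake is consistent lenalidomide dosing after a hold. Lenalidomide is given in both arms, so any randomized patient could be affected.

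**Working it through.** **Step 1: list the cells.** These are all the lenalidomide entries in 5.5.3 with the Day 14 wording. Each recovery level is an alternative to return to baseline.

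| Row | Grades stated in the row | Includes grade 3 or 4 | Recovery level for lenalidomide | Ixazomib/placebo cell |
|---|---|---|---|---|
| Neutropenia | 3 (sustained or with fever), 4 | yes | 2 or less | restart, rest of cycle, 2 or less |
| Thrombocytopenia | 3 (sustained or with bleeding), 4 | yes | 2 or less | restart, rest of cycle, 2 or less |
| Infection, normal neutrophils | 2 or higher | yes | 1 or less | restart, rest of cycle, 1 or less |
| Non-blistering rash | 2-3 | yes | 1 or less | restart, rest of cycle, 1 or less |
| Arrhythmia | 2 | no | 1 or less | no modification |
| Allergic reaction | 2-3 | yes | 1 or less | restart, rest of cycle, 1 or less |
| Constipation | 3 or higher | yes | 1 or less | dose maintained |
| CrCl below 30 mL/min | none stated | not stated | 1 or less | no modification |
| Any other non-hematologic | 3 or higher | yes | 2 or less | restart, rest of cycle, 2 or less |

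The counts are nine cells with the Day 14 wording, seven that include grade 3 or 4, and three with a recovery level of grade 2 or less. The neutropenia row also lets the lenalidomide dose be maintained with G-CSF, which does not affect the counts.

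**Step 2: compare Day 14 with the schedules.** Full-dose treatment ends on Day 28 (5.1.1, 8.2.5). The levels in 5.5.2 are 21 days in every 28, daily for 28 days, or every other day for 28 days. None ends on Day 14. This mismatch applies to all nine cells and does not depend on 5.5.

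**Step 3: compare with 5.5.** Its rule covers grade 3 and 4 events, so it reaches the seven cells. It differs from them in three ways.

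- End of dosing: what is left of the cycle in 5.5, Day 14 in the table.
- Timing of recovery: before the next scheduled dose in 5.5, before Day 14 in the table. For a drug taken daily, the next scheduled dose is the next day. Read literally, 5.5 then covers only recovery before that dose and gives no in-cycle instruction for slower recovery. Read loosely, it covers any recovery within the cycle. The text does not settle which.
- Recovery grade: grade 1 or less in 5.5, grade 2 or less in three of the seven rows.

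**Step 4: size within one cycle.** Doses lost by stopping at Day 14 are the scheduled doses after Day 14. Day 14 itself is counted as a dosing day, and the 21 days are taken as Days 1-21, which 5.5.2 does not specify.

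- 21-day level: 21 - 14 = 7 doses, and 7/21 = 33% of that level's doses per cycle.
- Daily 28-day level: 28 - 14 = 14 doses, and 14/28 = 50%.
- Every-other-day level: 14 doses per cycle, 7 of them after Day 14, and 7/14 = 50%.

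In both columns of 5.5.2 the first reduction lands on a 21-day level, so the 7-dose figure applies to a first reduction. The 14-dose figure arises only from the second reduction on. The day of restart does not change the difference, because the two readings share every dose up to Day 14.

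**The case against.** The strongest reply is that the table governs. Section 5.5 points to the tables for the events that need modification, and several rows for grade 3 or higher events openly depart from its general rule. Thrombosis restarts at the same dose level. Grade 3-4 arrhythmia and erythema multiforme end lenalidomide. The thyroid row, which states no grade, omits the drug until the next cycle. Such rows would have little purpose if 5.5 prevailed. This argument carries weight: if rows govern, the difference from 5.5 largely falls away. Precedence is still not stated, and the mismatch between Day 14 and the schedules in 5.1.1, 5.5.2 and 8.2.5 remains.

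The Day 14 limit could also be a deliberate rest for the second half of the cycle, with late recovery waiting for the next cycle. That is possible, but the cells do not say so, and their heading runs to Day 21.

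Three stronger readings are tempting and are not supported.

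- A reader might infer that the grade 2 recovery level is a lenalidomide slip. The same three rows use it for both drugs, so it looks specific to the toxicity. It conflicts with 5.5 only if 5.5 prevails.
- A reader might take the ixazomib/placebo column as proof of an error. That drug is dosed on Days 1, 8 and 15, so different wording is no contradiction. Nor do all its restarts run for the rest of the cycle: the neuropathy row sets no such period.
- A reader might infer that patients would cross the 75% relative dose intensity cutoff in 9.3.3. Planned dose intensity is not defined in 9.2.1.3, and 9.3.3 gives no time window for the lenalidomide classification. Measured against the starting schedule, a 21-day level gives 21/28 = 75%, exactly on the cutoff, so almost any lost dose could move a patient. No effect can be attributed to the Day 14 wording on this basis.

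**Conclusion.** The point stands as a wording inconsistency that should be corrected. Nine cells use a restart window and a stop day that fit no lenalidomide schedule in the protocol, and they give no in-cycle instruction for recovery on Day 14 or later. Seven of the nine also differ from 5.5 for grade 3-4 events. Three of those seven differ on recovery grade, which is a conflict only if 5.5 prevails. The counts rest on the grades printed in the table. The CrCl row prints none and is therefore not placed under the 5.5 rule.

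The size is 7 or 14 doses in the affected cycle, under the day-counting assumptions above. The documents give no rate for such holds, so no trial-wide total can be stated. Both arms follow the same lenalidomide rules, and no effect on OS, PFS, the comparison between arms or the ixazomib adherence interim is shown.

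**What to change.** Reconcile 5.5 and the nine cells of 5.5.3 with 5.1.1, 5.5.2 and 8.2.5, so that the lenalidomide restart window and last dosing day match its schedule. In the same edit:

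- state what happens in the cycle when recovery comes on Day 14 or later;
- say what the next-scheduled-dose condition in 5.5 means for a daily drug;
- state whether table rows override 5.5, including on recovery grade.

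Which window, stop day and recovery grade apply is a clinical choice for the study team. The cost is amendment text in one section and one table, with no extra patients or procedures.

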3.2 Step 1 Randomization

Rev. Add3

- _____ 3.2.1 Patient must meet all eligibility criteria in Section [3.1](#) at the time of Step 1 randomization.
- _____ 3.2.2 Patient must not be off lenalidomide maintenance therapy for more than 30 days prior to start of treatment on Step 1 of this protocol.

_____ 3.2.3 Patient must have evidence of residual disease by central MRD testing or by presence of monoclonal protein in serum or urine.

_____ 3.2.4 Patient must have SPEP, UPEP, and serum FLC performed \leq 28 days prior to randomization.
Serum M-protein by SPEP _____ (g/dL)
Date of Test: _____
Urine M-protein light chain excretion by UPEP _____ (mg/24hr)
Date of Test: _____
NOTE: UPEP (on a 24-hour collection) is required, no substitute method is acceptable. Urine must be followed monthly if the baseline urine M-spike is \geq 200 mg/24 hr. Please note that if both serum and urine M-components are present, both must be followed in order to evaluate response.

Serum Free Light Chain
Kappa FLC _____ (mg/dL) or _____ (mg/L);
Lambda FLC _____ (mg/dL) or _____ (mg/L);
Kappa/lambda ratio _____
Date of Test: _____

_____ 3.2.5 Patient must have the following laboratory levels obtained \leq 14 days prior to randomization:

_____ 3.2.5.1 Hemoglobin \geq 8 g/dL
Hemoglobin: _____ Date: _____

_____ 3.2.5.2 Untransfused platelet count \geq 75,000 cells/mm³
Platelet: _____ Date: _____

_____ 3.2.5.3 Absolute neutrophil count (ANC) \geq 1000 cells/mm³
ANC: _____ Date: _____

_____ 3.2.5.4 Calculated creatinine clearance \geq 30 mL/min
Creatinine clearance: _____ Date: _____

_____ 3.2.5.5 Total bilirubin \leq 1.5 times the upper limit of normal (ULN)
Total bilirubin: _____ ULN: _____ Date: _____

_____ 3.2.5.6 SGPT (ALT) and SGOT (AST) \leq 3 times the upper limit of normal (ULN)
SGPT (ALT): _____ ULN: _____ Date: _____
SGOT (AST): _____ ULN: _____ Date: _____

_____ 3.2.6 Patient must not have Grade 2 or higher peripheral neuropathy or grade 1 peripheral neuropathy with pain per CTCAE.

_____ 3.2.7 Patient must not have uncontrolled intercurrent illness.

_____ 3.2.8 Patient must not have Grade 2 or higher diarrhea per CTCAE in the absence of antidiarrheals.

_____ 3.2.9 Patient must not have been on systemic treatment, within 14 days before the first dose of ixazomib, with strong CYP3A inducers (such as rifampin, rifapentine, rifabutin, carbamazepine, phenytoin, phenobarbital), or use of St. John's wort.

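### Table 5.5.3, peripheral neuropathy row: the middle grade band has no upper limit, so grade 4 falls under two different ixazomib/placebo instructions

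*Combined protocol and SAP*

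**What the plan says.** Section 5.5.3 sets dose changes by toxicity, with one column for events attributed to lenalidomide and one for events attributed to ixazomib/placebo. Because the trial is blinded, both arms follow the same row.

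The peripheral neuropathy row has three grade lines. The first covers painless grade 1 or 2. The second and third appear in the text as "Grade >2 or grade 2 with pain Grade 4", which runs across the break between the two lines.

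The ixazomib/placebo column gives three actions in the same order: reduce by one level; "Discontinue ixazomib/placebo until toxicity resolves or returns to baseline. When toxicity resolves, re-initiate ixazomib/placebo at the next lower dose level"; and, for grade 4, discontinue, with no further words.

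Elsewhere in the same column, the grade 4 allergic reaction line reads "Discontinue ixazomib/placebo and do not resume".

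**The concern.** Grade 4 is greater than grade 2, so it satisfies the second line as well as its own. The two lines differ on the matter that counts most after a grade 4 event, which is whether the drug may be given again.

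Eligibility criterion 3.2.6 states "Patient must not have Grade 2 or higher peripheral neuropathy or grade 1 peripheral neuropathy with pain per CTCAE", so baseline for a randomized patient is at worst painless grade 1. Under the second line, a patient who recovered from grade 4 to that state would restart ixazomib/placebo one level lower. Under the third line the drug is stopped. What is at stake is uniform application of a safety rule for a toxicity that the plan also studies as a primary patient-reported objective (2.4.1.1). No statistical quantity depends on it.

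**Working it through.** No arithmetic applies, so the check is a reading of the row against the rest of the table.

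**Step 1. Match grade lines to ixazomib/placebo actions.**

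| Grade line (paraphrased) | Ixazomib/placebo action (paraphrased) |
|---|---|
| 1 or 2, no pain | Reduce one level |
| Above 2, or 2 with pain | Stop, then restart one level lower after recovery |
| 4 | Discontinue, unqualified |

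The line breaks were lost when the text was extracted. Three labels still match three actions in order in this column, and the overlap comes from the greater-than sign, not from the layout. The lenalidomide column shows only two actions, both worded "Reduce dose of lenalidomide to the next lower dose level. If a patient is already at the lowest drug level, go off treatment", so the one-to-one match can be claimed for the ixazomib/placebo column only.

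**Step 2. Place each grade.** Painless grade 1 or 2 meets the first line only. Grade 2 with pain meets the second only. Grade 3 meets the second only. Grade 4 meets the second and the third.

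**Step 3. Compare with the other rows split by grade.**

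| Row | Bands | Overlap |
|---|---|---|
| Non-blistering rash | 2-3, then 4 | None |
| Cardiac arrhythmia | 2, then 3-4 | None |
| Allergic reaction | 2-3, then 4 | None |
| Constipation | 1-2, then 3 or higher | None |
| Peripheral neuropathy | above 2 (or 2 with pain), then 4 | Grade 4 |

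Neuropathy is the only row whose bands overlap. The two rows that give grade 4 a line of its own, rash and allergic reaction, both cap the band above it at grade 3.

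**Step 4. See whether the verb settles it.** In the ixazomib/placebo column the verb for stopping appears three times: expressly permanent (grade 4 allergic reaction), expressly temporary (neuropathy, second line) and unqualified (neuropathy, grade 4). The temporary use sits directly above the unqualified one in the same cell. The column alone therefore does not define the term, although wider usage in the protocol points to a permanent stop, as set out in the objection.

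**The case against.** The strongest reply is that the row resolves itself, and most of that reply stands.

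- If grade 4 followed the second line, a separate grade 4 line would have no purpose. The specific line therefore governs.
- The table's usual term for a temporary stop is a hold or interruption. The one temporary use of the stronger verb carries an express qualifier, and the grade 4 line does not.
- Unqualified uses elsewhere read as final: four of the five lenalidomide uses in table 5.5.3, the bottom step of the ixazomib/placebo ladder in 5.5.1, and the bottom step of the reduced-renal-function lenalidomide ladder in 5.5.2. None of these six is tied to a restart. The absence of an explicit bar on resuming is therefore weak evidence by itself.
- There are backstops. Section 5.5 ends study treatment after a toxicity delay of more than 8 weeks (whether this covers a hold of one drug is arguable), section 5.7 ends it for unacceptable toxicity, and section 5.3.7 requires 24-hour notification of grade 4 events.

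Three stronger readings are tempting, and the documents do not support them.

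- A reader might infer that section 5.5 itself authorizes re-challenge after grade 4, since it covers "Patients experiencing grade 3 or 4 AE's that are possibly, probably or definitely related to a particular agent(s) requiring dose modifications" and says "treatment should be restarted with a one dose level reduction for the causative drug for the remainder of the cycle". That sentence goes on to defer to the tables, which have a grade 4 entry for neuropathy, and the restart is conditional on recovery before the next scheduled dose.
- A reader might estimate the number of patients affected from the ixazomib-lenalidomide maintenance study in section 1.3, which reports 6 of 64 patients with grade 3 neuropathy and lists no grade 4. Any bound from those data concerns the incidence of grade 4, not the number wrongly restarted. Grade 3 patients are outside the overlap.
- A reader might infer that the lowest-dose instruction in this row leaves open whether both drugs stop. The columns are drug-specific, section 5.5 confines reduction to the drug held responsible, and 5.5.1 already lists discontinuation below the lowest ixazomib/placebo dose.

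What survives is narrow: the label itself is misstated. A site can reach the right answer, but only by inference.

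**Conclusion.** The point holds as a drafting error in a safety rule. On its wording the neuropathy row gives two ixazomib/placebo instructions for grade 4, and the other rows of the table show how this should have been avoided. The grade 4 line almost certainly controls, so wrongful re-challenge is unlikely; it would need a grade 4 event, recovery to baseline, and an investigator who passes over the line labelled for that grade.

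Severity is minor. No endpoint, power, alpha, sample size or analysis changes, and the documents do not support a count of patients affected. The conclusion rests on one assumption, that the three ixazomib/placebo actions match the three grade lines in the order printed.

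**What to change.** Relabel the second neuropathy line as grade 3, or grade 2 with pain. Word the grade 4 ixazomib/placebo action "Discontinue ixazomib/placebo and do not resume", as in the grade 4 allergic reaction line. Grade 3 and painful grade 2 keep the present stop-and-restart rule.

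When the row is edited, check in the typeset table that grade 4 attributed to lenalidomide still has an action once the band is capped. The extracted text does not show which grade lines the two lenalidomide actions belong to.

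The cost is one table row by amendment and a memo to sites. No patients, procedures or statistics change.
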